Procedures: N=40 parent/child dyads will receive a weekly monetary incentive for losing weight during an initial 12 week weight-loss program. During this time, half of the families will receive EFT training (N=20) and the other half will receive a control thought training program (N=20). After 12 weeks, the monetary incentives program will be terminated, but the parent/child dyads will continue their respective EFT or control thought training programs for an additional 12 weeks. At the end of the additional 12 weeks, weight-loss maintenance will be examined between dyads that received EFT and dyads that received control thought training.

Procedures Cohort 2:

Procedures: N=20 parent/child dyads will receive a weekly monetary incentive for losing weight during an initial 8 week weight-loss program. During this time, half of the families will receive EFT training (N=10) and the other half will receive a control thought training program (N=10). After 8 weeks, the monetary incentives program will be terminated, but the parent/child dyads will continue their respective EFT or control thought training programs for an additional 8 weeks. There will then be an 8 week no intervention follow-up period. At the end of the follow-up period, weight-loss maintenance will be examined between dyads that received EFT and dyads that received control thought training.

Purpose (Cohort 3): To assess whether episodic future thinking (EFT), thought training that teaches individuals to think prospectively about future events as if they were happening now, promotes healthier grocery shopping behaviors in parent and child dyads in which the child is obese/overweight, and to assess subsequent weight loss.

Procedures Cohort 3:

N=6-12 parent/child dyads will receive the full family-based therapy program with a specialized EFT component focused on grocery shopping during this 15 week weight-loss program. This study is a nonconcurrent multiple baseline design; participants will be randomized to a 4 week, 7 week, or 10 week group with staggered baseline periods followed by 4-8 weeks of the intervention consisting of FBT and EFT.

1.4 Specify your research question(s), study aims or hypotheses: We hypothesize that:

1) Parent/child dyads in both the EFT and the CONTROL thought training conditions will lose weight with the monetary incentive program.

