2) Parent/child dyads in the EFT condition will have greater weight-loss maintenance than parent/child dyads in the CONTROL thought training program when the monetary incentive program is terminated.

Cohort 3: Aim 1: To examine whether EFT will lead to healthier grocery shopping behavior. Aim 2: To test the influence of EFT on Delay Discounting (DD).

H1: We hypothesize that EFT will improve healthy grocery shopping behaviors. H2: We hypothesize that EFT will reduce DD.

1.5 Background and significance and/or Preliminary studies related to this project:

Monetary incentive programs have been shown to be effective at reducing weight in the short-term [Leahey, John, Volpp, Ries]; however, numerous studies have demonstrated that individuals often regain weight when incentive programs are terminated [John, Volpp, Reis]. This behavioral change relapse is unsurprising; it is well-established that a specific behavior is often extinguished when reinforcement for that behavior is removed. It is unlikely, then, given the expense, that monetary incentive programs could be implemented long-term for chronic diseases like obesity where lasting behavioral changes are essential. Thus, programs are needed to bridge the gap between the successful short-term weight-loss effects of a monetary incentive program and long-term weight-loss maintenance after the incentives are removed.

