The following surveys from the full protocol will be collected via Qualtrics and will not contain any PHI: Parent: Consideration or Future Consequences Scale, Delay Discounting Task, Living to 75 Assessment, Palatable Eating Motives Scale

Child: Consideration or Future Consequences Scale, Delay Discounting Task, Living to 75 Assessment, Palatable Eating Motives Scale

Cohort 3 - Due to the COVID 19 outbreak, in-person assessments and interventions are no longer feasible. Therefore, the researchers will carry out these study components remotely. The programs that will be used are phone, Zoom, and Qualtrics.

WEEK 0 - Baseline Session: ~ 2 hours; In-Lab Group Session - All Baseline sessions were completed as planned in lab.

First, upon arriving to the lab, each dyad will be escorted to a private room and will complete the following: 1- Have height and weight measured.

2- Complete surveys: Consideration of Future Consequences Scale (CFCS), EDE-Q (Parent), KEDS (Child)

3- Complete the Delay Discounting Task, the Virtual Shopping Task, and Home Food Inventory. A letter was sent to each family explaining the change from in-home visits with the Cupboard inventory to the self-completed Home Food Inventory, due to growing concern over COVID-19.

4- Receive first assessment payment (\$40 dollars)

Following steps 1-4, the families will take part in a group session to learn the core components of the program in presentations by the research staff.

Weeks 1-14 \sim 2 hours; Weekly In-Lab Group Sessions - Due to the COVID 19 outbreak, in-person assessments and interventions are no longer feasible. Therefore, the researchers will carry out these study components remotely. The programs that will be used are phone, Zoom, and Qualtrics.

1. The day of their assigned parent group session, each family will email the study coordinator a photocopy of their food receipts, receipt forms, and food log. They will self-report weights via email as well. Payment will be completed via check request, Amazon Pay, or Forte.

2. Children will join a child-only Zoom group video session, and parents will join a parent-only Zoom video session. Each group will be led by a study team member. In these sessions, participants will do the thought training program, and talk to staff and other group members about progress in the program. Each parent-child dyad will meet via Zoom or phone at a separate time with a study team member to complete the case management portion of the program.

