a. During the 15-week intervention, participants will be asked to log their activity related to the program in food logs. b. Researchers will access the information and send feedback to the participants (via text, phone, and/or email) to help them succeed in the program.

Throughout the baseline period, the study team will assess all participants' adherence levels through looking at data from the food logs and the collected receipts.

Once a family has been determined to be adhering to the study protocol, the participant will then be randomly assigned to either the 4-week, 7- week or 10-week baseline group. Participants who were assigned 4- week baseline, will now be eligible to start the intervention, those in the 7-week will complete three more weeks of baseline prior to the intervention.

An assessment session will take place the week the group starts the intervention, which will consist of

1- Self-reported weights via email

2- Complete surveys: EDE-Q (Parent), KEDS (Child) on Qualtrics

3- Complete EFT cue generation needed for thought training – See cohort 2 for description – this will be remotely done via Qualtrics.

4- Complete the Delay Discounting Task on Qualtrics and the Virtual Shopping Task via emailed instructions.

5- Review weekly receipts and receive receipt payment if applicable (\$25 dollars) via check request, Amazon Pay or Forte.

6- Receive assessment session payment (\$40 dollars) via check request, Amazon Pay or Forte.

7. Receive a EFT Cue Retrieval technology tutorial via emailed instructions, or a Zoom or phone session as requested – See cohort 2 for description.

Assessment measures must be completed the day of their assigned group sessions. Child and Parent Zoom-based group sessions will be conducted at their scheduled times, as well as scheduled case management.

Week 15 \sim Final Assessment - All assessment measures for week 15 will be conducted remotely, unless COVID-19 related restrictions are lifted, in which an in-lab visit for final measurements may be conducted.

1- Self-reported heights and weights

2- Complete surveys on Qualtrics: Consideration of Future Consequences Scale (CFCS), EDE-Q (Parent), KEDS (Child), Formative Questionnaire, TT Frequency of Use

3- Complete the Delay Discounting Task, Shelf Life Inventory, and Home Food Inventory on Qualtrics, and the Virtual Shopping Task via emailed instructions.

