Secondary analyses: A two-way repeated measures ANOVA will be conducted to determine differences in delay discounting between the EFT and HT groups over time. Data points will be collected at sessions 2 (baseline), 11 (incentive program ends), 19, and 20. We hypothesize:

1- The EFT group will have a reduction in delay discounting over time (11, 19, 20) compared to baseline.

2- The HT group will not have a reduction in delay discounting over time (11, 19, 20) compared to baseline.

3- The EFT vs. the HT group will have a reduction in delay discounting over time (11, 19, 20).

Regression analyses will also be conducted to determine whether baseline characteristics predict outcome variables (BMI for adults/percent over BMI for children, weight, and DD). These characteristics will be collected from baseline surveys including the Consideration of Future Consequences Scale, Living to 75 Assessment, and Palatable Eating Motives Scale. First, zero order correlations between each predictor and the outcome variables will be established, and then significant predictors will be entered in a multiple regression model that includes demographic characteristics predict child and adult success. In addition, we will assess the influence of parental success on child success in a multiple regression model, again controlling for demographic characteristics.

The results of this study will be analyzed graphically as well as assessing the degree of change from baseline to treatment across the three replications.

1.23 Provide the rationale or power analysis to support the number of participants proposed to complete this study. This is the first study of this kind, therefore, we were unable to conduct a power analysis. Additionally, a power analysis is not applicable to this multiple baseline design. We are collecting weekly data from participants and will have enough data points to ensure we will be able to achieve the study objectives. The results of this study will be analyzed graphically as well as assessing the degree of change from baseline to treatment across the three replications. For an example of a study that utilized a multiple baseline design, see:

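### In Cohort 3, delay discounting is measured three times per family and never in a study week with both treated and untreated families, so the weekly-data rationale in 1.23 does not cover Aim 2

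*Combined protocol and SAP*

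**What the plan says.** Section 1.4 states for Cohort 3: "H2: We hypothesize that EFT will reduce DD". Section 1.3 describes the design: "This study is a nonconcurrent multiple baseline design", in which "participants will be randomized to a 4 week, 7 week, or 10 week group with staggered baseline periods".

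Section 1.13 (Cohort 3) schedules the tasks as follows.
- Week 0: "3- Complete the Delay Discounting Task, the Virtual Shopping Task, and Home Food Inventory".
- Start of EFT: "An assessment session will take place the week the group starts the intervention". DD (on Qualtrics) and the Virtual Shopping Task (by emailed instructions) are on its list, after EFT cue generation.
- Week 15: "3- Complete the Delay Discounting Task, Shelf Life Inventory, and Home Food Inventory on Qualtrics", with the Virtual Shopping Task again by email.

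The items collected weekly are receipts, food logs and weights that families report themselves. Section 1.23 then says: "We are collecting weekly data from participants and will have enough data points to ensure we will be able to achieve the study objectives". The Cohort 3 analysis in 1.22 and 1.23 consists of graphs and the size of the change from baseline to treatment. It specifies no model for time.

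**The concern.** A staggered-baseline design is persuasive when the outcome shifts as each family's own intervention begins and stays level in baselines of other lengths. That needs either repeated points within each phase or treated and untreated families measured at the same stage. The weekly receipts supply both. DD supplies neither: a family with a 10-week baseline yields no more DD points than one with a 4-week baseline.

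What is at stake is the reading of H2. A fall in DD by Week 15 would be credited to EFT on the strength of the multiple baseline label, although the DD schedule makes almost no use of the staggering. The same limit applies to the Virtual Shopping Task, which 1.4 does not name as the outcome of either aim.

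**Working it through.** **Inputs.** EFT starts at week 4, 7 or 10, with 6 to 12 families (1.3). DD is taken at Week 0, the start week and Week 15 (1.13). The payments in 1.13 agree: three assessments, 40 + 40 + 45 = 125; weekly receipts, 25 × 15 = 375; total 500. The within-family residual SD (σ) is not given, so standard errors are in units of σ. Equal groups (2 or 4 families each) are assumed.

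**DD schedule as written.**

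| Study week | 4-week group | 7-week group | 10-week group | Both states measured? |
|---|---|---|---|---|
| 0 | untreated | untreated | untreated | no |
| 4 | start week | – | – | no |
| 7 | – | start week | – | no |
| 10 | – | – | start week | no |
| 15 | treated | treated | treated | no |

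The count is 0 of 5. It stays at zero if actual start weeks move, because between Week 0 and Week 15 a family takes DD only at its own phase change.

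**What can be estimated.** Take DD = family effect + time effect + β × treated + error. Then SE(β) = σ/√RSS, where RSS is the residual sum of squares of the treated indicator after regression on the family and time terms.

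- *No time effect.* If the start-week DD precedes EFT, each family's indicator is 0, 0, 1. RSS per family is (1/3)² + (1/3)² + (2/3)² = 2/3. Six families give RSS = 4 and SE = 0.500σ; twelve give RSS = 8 and SE = 0.354σ.
- *A free effect for each week.* If the start-week DD precedes EFT, the treated indicator is identical to the Week 15 indicator. If it follows EFT, it is one minus the Week 0 indicator. Either way RSS = 0 and β cannot be estimated, whatever the number of families.

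SE/σ for 6 / 12 families, start-week measurement taken as before EFT:

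| Time assumption | DD as scheduled | DD at 0, 4, 7, 10, 15 in all | Weekly receipts, weeks 1–15 |
|---|---|---|---|
| none | 0.500 / 0.354 | 0.395 / 0.280 | 0.224 / 0.158 |
| linear | 1.012 / 0.715 | 0.678 / 0.480 | 0.389 / 0.275 |
| quadratic | 3.484 / 2.464 | 0.694 / 0.491 | 0.391 / 0.276 |
| free weeks | not estimable | 0.732 / 0.518 | 0.423 / 0.299 |

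If the start-week DD counts as after EFT, the DD-as-scheduled column becomes 0.900 / 0.636 (linear) and 2.617 / 1.851 (quadratic); its other rows do not change.

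**What a wrong time assumption does.** With the start-week DD before EFT, every post-EFT value falls at Week 15. A one-unit shift after week 10 that has nothing to do with EFT is then reported as an EFT effect of 1.0, both in a pre-post comparison and with a linear trend.

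**Mixed-status weeks.** Receipts have both states observed in weeks 5 to 10 (4 to 9 if the start week counts as treated). A common DD grid would give weeks 7 and 10 (4 and 7 if DD follows cue generation).

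**Intervention length.** From the starts to Week 15 is 15 − 4 = 11, 15 − 7 = 8 and 15 − 10 = 5 weeks. Section 1.3 gives 4 to 8 weeks.

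**The case against.** The design is declared nonconcurrent, so the documents do not promise measurement of treated and untreated families side by side. The inference is meant to come from change within families, replicated across three baseline lengths. If the start-week DD precedes EFT, the groups also show untreated change over 4, 7 and 10 weeks, which bears on drift and on one repeat of the task. With a linear trend the effect is estimable. A reader might infer that Aim 2 cannot be tested at all; the documents do not support that, because the failure is complete only when week effects are unrestricted. What remains is that no time model is planned, that nothing untreated is seen after week 10, and that the third administration is never seen in an untreated family.

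A reader might also infer that the move from lab to remote testing confounds every DD comparison. It affects comparisons with Week 0. The start-week DD is already remote, so start week to Week 15 is remote to remote if that DD precedes EFT and Week 15 stays remote. Section 1.13 lists cue generation before DD and allows a final lab visit, so neither condition is secured.

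Nor is 1.23 simply false, or Cohort 3 undermined as a whole. Weekly data are collected, and they serve grocery shopping, which 1.5 makes the primary purpose.

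On feasibility the objection largely stands. Section 1.12 says enrolment is complete, and 1.13 says all baseline sessions are done. In 1.15 the Home Food Inventory is dated 03/12/20 and the Shelf Life Survey 06/15/20, 95 days or 13.6 weeks apart, which suggests that weeks 4, 7 and 10 may have passed for many families.

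**Conclusion.** The point holds for DD, and so for Aim 2, and for the Virtual Shopping Task; it does not reach receipts, logs or weights. DD has three observations per family, one or two per phase, and no study week with mixed status. Under the planned analysis an EFT effect on DD cannot be separated from repeat testing, drift, continuing programme exposure or anything else that changes by Week 15. An estimate needs either no time effect (SE 0.500σ / 0.354σ) or a trend extrapolated to Week 15 (linear 1.012σ / 0.715σ; quadratic 3.484σ / 2.464σ), and the plan states neither assumption.

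This rests on a final assessment at Week 15 for every family, as 1.13 has it, and on weeks counted from each family's entry. Family start dates are not given, so chance calendar overlap cannot be excluded. The plan should be corrected, at least in what it claims.

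**What to change.** 1. In 1.23, limit the weekly-data statement to receipts, food logs and weights. In 1.4 and 1.22, describe the Cohort 3 DD result as an uncontrolled pre-post description that does not attribute change to EFT. This costs only wording and is due in any case.
2. In 1.13, state whether DD comes before or after cue generation in the start-week session.
3. For any family that has not yet passed those weeks, give the existing remote DD and Virtual Shopping tasks at weeks 0, 4, 7, 10 and 15 whatever the baseline length, with DD before cue generation in the start week. Weeks 7 and 10 then become mixed-status, and the step is estimable with free week effects (SE 0.732σ / 0.518σ if all families follow the grid).
4. Reconcile the intervention length in 1.3 with the 11, 8 and 5 weeks implied by 1.13.

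Item 3 means two more remote administrations per parent and child, and some added practice effect. If each were paid like an existing $40 assessment (an assumption), the cost is 2 × 40 = $80 per family, or $480 to $960 for 6 to 12 families. It may come too late for enrolled families. It would also not separate EFT from the family-based programme if both begin together: 1.3 describes the post-baseline intervention as containing both, while 1.13 has programme sessions from Week 0.
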